#### 4.2 Statistical Analysis Plan

This trial will be analyzed according to the intention-to-treat principle, and any subject who completes randomization will be followed up until the end of the trial (unless the subject withdraws informed consent). This study uses SPSS data analysis software for analysis. Quantitative data will be expressed as mean  $\pm$  standard deviation or median (interquartile range) depending on whether it conforms to the normal distribution; enumeration data will be expressed as frequency (percentage). Group patients according to intervention measures, compare differences between groups and express them as absolute standard deviations. Comparisons between groups are performed using the two independent sample t-tests for normally distributed measurement data, comparisons between groups are performed using the rank sum test for skewed measurement data, and comparisons between groups are performed using the  $\chi^2$  test for enumeration data. All tests are two-sided, and  $P < 0.05$  means the difference is statistically significant.

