### 3.2 Subject selection

#### 3.2.1 Inclusion criteria

- (1) Children aged 6-14 years old;
- (2) Children who have atrial septal defect or ventricular septal defect scheduled for lateral incision cardiac surgery with cardiopulmonary bypass;
- (3) Inform consent signed by the parent or legal guardian.

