### 3.4 Research process

#### 3.4.1 Research flow chart

#### 3.4.2 Research implementation (method, content, steps, etc.)

##### 1) Before surgery:

The investigator will conduct a pre-screening process to assess whether potential subjects are suitable for inclusion in this study. After pre-screening, the investigator will conduct a screening process to assess whether the subjects meet the inclusion criteria. Before the process of screening subjects, researchers need to obtain informed consent. Our assessment mainly collects the following information:

- A. Informed consent: When contacting the subject for the first time, the researcher should explain the entire process of the trial to the subject or their legal representative and obtain their informed consent;
- B. Demographic information: gender, date of birth, race, height and weight;
- C. Medical history: Medical history relevant to this study, including primary diagnosis, NYHA classification, diabetes, hypertension, hyperlipidemia, infective endocarditis,

COPD, peripheral vascular disease, cerebrovascular disease, previous cardiac surgery history, smoking history, allergy history and current medications (beta blockers, ACE inhibitors, ARBs, statins, diuretics);

D. Basic vital signs: body temperature, heart rate, blood pressure, oxygen saturation

E. Related examinations: echocardiography, routine blood tests, liver and kidney function tests, and coagulation function tests

2) Intraoperative:

Implementation of intervention: After the operation, patients in the experimental group and the control group were treated with drug A for paravertebral block, and drug B for local infiltration block through the incision. Paravertebral block is performed under ultrasound guidance, and right T4 paravertebral nerve block is performed. It is recommended to use the needle insertion method in the sagittal plane. Use 0.375% ropivacaine at a dosage of 3 mg/kg. The rest of the intraoperative anesthesia protocol is the same as the clinical routine.

Intraoperative anesthesia management: Give anesthetic drugs and perform intraoperative management according to the routine of the anesthesia center.

Intraoperative record information: basic intraoperative information such as type of operation, operation time, etc.

3) After surgery:

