### 3.6 Endpoint evaluation

#### 3.6.1 Effectiveness evaluation

1) Primary endpoint: total opioid consumption within 24 hours after surgery (ug/kg)

2) Secondary endpoints: other postoperative analgesic indicators.

A. FPS-R scores at 6 hours, 12 hours, 18 hours, and 24 hours after surgery. (See attachment 1)

B. Rates of postoperative opioid rescue analgesia use in both groups.

C. Time to first postoperative FPS-R  $\geq 4$  points (recorded by bedside nurse)

D. Postoperative mechanical ventilation time, ICU stay time, and postoperative hospitalization time

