### 3.7 Randomization method and blinding method

#### 3.7.1 Blinding

For children who signed informed consent and screened into the group, their baseline information is recorded, and randomization is conducted after entering the operating room. The children are randomly grouped using the block randomization method. After the random numbers are generated by the computer, all the random numbers are coded and sealed into opaque envelopes. The code, that is, the selection number, was written on the outside of the envelope, and the random number was placed inside the envelope. The children were randomly divided into the experimental group (PVB group) and the control group (local infiltration group). This study is blinded to the intraoperative anesthesiologists, patients, data collectors and analysts, and study result evaluators. Before surgery, a pharmacist who is not involved in the follow-up process opens the envelope and prepares medications based on the grouping results. The pharmacist prepares two medications, A and B for each patient. Drug A for patients in the test group is 3 mg/kg of 0.375% ropivacaine, while for patients in the control group, drug A is the same volume of normal saline. Drug B for patients in the control group is 0.375% ropivacaine at 3 mg/kg, and drug B for patients in the test group is the same volume of normal saline. The anesthesiologists all use drug A to perform paravertebral block on the patients, and drug B to perform local infiltration on the patients. The intraoperative anesthesia management plans of the two groups of patients are exactly

the same, so they are blinded. All patients undergo paravertebral block and local infiltration twice, so they are blinded. The anesthesiologists who collect intraoperative and postoperative data do not know the patient grouping information, so they are blinded. The ICU nurse who evaluates the patient's postoperative pain and adds analgesics does not know the patient's group information and is therefore blinded.

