## 4. Statistical considerations

### 4.1 Sample size estimation

Sample size calculation is based on the primary outcome, total opioid consumption within 24 hours after surgery. Referring to the preliminary test results, the average total opioid consumption within 24 hours after surgery in the traditional low-dose opioid anesthesia group was  $850 \pm 180 \text{ } \mu\text{g/kg MSE}$ . According to previously published literature (12, 13) and the experience of clinical experts, it is assumed that in the PVB group, total opioid consumption within 24 hours after surgery was reduced by an average of 30%,  $255 \text{ } \mu\text{g/kg MSE}$ . At the same time, the combined standard deviation was conservatively estimated to be  $425 \text{ } \mu\text{g/kg MSE}$ . When the significance level of the

statistical test was taken to be one-sided 0.025, the power level was taken to be 80%. hour. According to statistical principles, 45 children need to be enrolled in each group, and the total number of cases in the two groups is 90. Sample size calculation was performed using the PASS software. Taking into account the maximum possible dropout rate of 10% in the study, this trial will eventually enroll 100 children, 50 children in each group.

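### The primary comparison ignores age and defect type, both recorded before randomisation; pre-specified adjustment would be a cheap gain in efficiency, not the repair of an error

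*Combined protocol and SAP*

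**What the plan says.** Section 4.2 has one generic rule for quantitative data and no separate rule for the primary outcome: "Comparisons between groups are performed using the two independent sample t-tests for normally distributed measurement data", and a rank-sum test when the data are skewed. It names no regression model, covariate or stratified test.

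The covariates are already collected. Section 3.4.2 (Before surgery) lists "Demographic information: gender, date of birth, race, height and weight" and, under medical history, the primary diagnosis. Section 3.7.1 has baseline information recorded first and randomisation done after entry to the operating room.

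The population is children aged 6 to 14. Section 3.2.1 admits "Children who have atrial septal defect or ventricular septal defect scheduled for lateral incision cardiac surgery with cardiopulmonary bypass", and the Abstract also allows both repairs in one child.

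On allocation, section 3.7.1 says "The children are randomly grouped using the block randomization method" and gives no stratification factor. Section 3.7.2, although headed as the randomisation method, describes only blinding. That allocation is unstratified is therefore an inference from silence.

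Section 3.1 promises a detailed statistical analysis plan before data analysis starts, but does not say whether it will adjust.

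**The concern.** Neither the design nor the analysis takes account of age or defect type. If either predicts opioid use, two things follow. The variance it explains stays in the error term, so the confidence interval is wider than it need be. Any chance imbalance between arms of about 45 also stays in the point estimate. Adjusting for a few baseline variables fixed in advance addresses both, preserves the type I error and needs no new data. It does not require a baseline measurement of the outcome, only a baseline variable that predicts it.

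The trial is sized almost exactly at its target, and the 10% enrolment margin is set aside for dropout. On the plan's own assumptions there is little slack, so a few points of power at almost no cost are worth having.

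**Working it through.** **Inputs from section 4.1.** Control mean 850; the plan assumes that "total opioid consumption within 24 hours after surgery was reduced by an average of 30" per cent, so the difference is 0.30 × 850 = 255 µg/kg. Sizing SD 425; preliminary SD 180. The "statistical test was taken to be one-sided 0.025, the power level was taken to be 80" per cent. Section 4.2 says "All tests are two-sided" at 0.05, which has the same critical value as one-sided 0.025. There are 45 evaluable children per arm.

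**Step 1: reproduce the plan (unadjusted t-test, noncentral t).**
- SE = 425 × √(2/45) = 89.6
- Noncentrality = 255 / 89.6 = 2.846; 88 df; critical value 1.987
- Power = 80.4%. With 44 per arm it is 79.5%, so 45 is the smallest size that reaches 80%.
- Allowing for 10% dropout: 45 / 0.90 = 50 per arm.

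The stated sample size reproduces.

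**Step 2: adjust for two covariates (age, defect type).** Let R² be the share of outcome variance that they explain together. Two costs are charged: 2 degrees of freedom (90 − 2 − 2 = 86; critical value 1.988), and the expected variance inflation from chance imbalance of the covariates between arms, 1 + 2/(90 − 2 − 3) = 1 + 2/85 = 1.0235.

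SE = 425 × √[(1 − R²) × (2/45) × 1.0235]; noncentrality = 255 / SE. The equivalent change in sample size is 1 / [(1 − R²) × 1.0235] − 1.

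The documents give no R², so the range is an assumption.

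| Assumed R² | SE | Noncentrality | Power | Equivalent change in sample size |
|---|---|---|---|---|
| Unadjusted | 89.6 | 2.846 | 80.4% | – |
| 0 | 90.6 | 2.813 | 79.4% | −2% |
| 0.05 | 88.4 | 2.886 | 81.4% | +3% |
| 0.10 | 86.0 | 2.965 | 83.4% | +9% |
| 0.20 | 81.1 | 3.145 | 87.5% | +22% |

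These figures use the model-based variance under equal spread in the two arms.

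**Step 3: break-even.** Adjustment pays once (1 − R²) × 1.0235 falls below 1, that is, for R² above about 0.023; the lost degrees of freedom add very little. At R² = 0.025 power is 80.4%, the same as unadjusted.

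**Step 4: the preliminary SD.** With SD 180, the unadjusted SE is 180 × √(2/45) = 37.9, noncentrality is 255 / 37.9 = 6.72, and power exceeds 99.99%. Adjustment then has no power left to add.

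**Step 5: the rank-sum route.** Under section 3.4.2 (After surgery) the opioid infusion starts only at FPS-R ≥ 4, and the rate of opioid rescue is a separate secondary endpoint. Zeros and skew are therefore possible, and the plan's own rule would then lead to the rank-sum test. The table compares a mean-difference model with a t-test and says nothing about that route.

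**The case against.** The case against is substantial.

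- **No error is shown.** A reader might infer that the planned test is biased or underpowered. It is neither. Under randomisation the unadjusted test is valid, its confidence interval already allows for chance imbalance, and the plan meets its own power target. This stands.
- **The gain is assumed.** Nothing in the documents links age or defect type to opioid use, and there are reasons to expect a small R². The outcome is already per kilogram, the infusion is dosed by weight, and all children have a lateral incision and the same block procedure. This stands. What remains is the asymmetry between a small bounded loss and a larger possible gain.
- **Adjustment is not free.** A reader might infer that it can only help. With unprognostic covariates it costs about 1 point of power.
- **Weight is also recorded.** A reader might want it in the model. Because the outcome is already divided by weight, it need not be included.
- **A mean regression could replace both tests.** A reader might infer this as the simplest remedy. It would change what is tested whenever the plan would have used the rank-sum test, and the figures above do not support that step.
- **A detailed plan is still to come.** It may supply the adjustment. Section 3.1 does not say that it will, so the gap stands for now, and that plan is the natural place to fill it.

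**Conclusion.** The point holds as a cheap improvement. The primary analysis is unadjusted although two plausible covariates are recorded before randomisation and no stratification is described. On the t-test route, with 45 per arm, a difference of 255 and SD 425, pre-specified adjustment moves power from 80.4% to between 79.4% and 87.5% as the assumed R² runs from 0 to 0.20. The downside is about 1 point of power, or about 2% of efficiency. The gain is immaterial if the true SD is near 180, and it is unquantified on the rank-sum route. The documents support neither a finding that the planned analysis is wrong nor any change in sample size.

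**What to change.** Before unblinding, in section 4.2 or in the detailed plan promised in section 3.1:

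1. Name age (years) and defect type (ASD only versus any VSD) as the only covariates for the primary outcome.
2. Where the plan uses the t-test, fit a linear regression of 24-hour opioid consumption (µg/kg) on arm, age and defect type with heteroscedasticity-robust standard errors. Report the adjusted mean difference with its 95% CI.
3. If the outcome is skewed or has many zeros, use a covariate-adjusted rank analysis (rank ANCOVA) with the same two covariates as the counterpart of the rank-sum test.
4. Keep the unadjusted t-test and rank-sum test as sensitivity analyses.

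The cost is one paragraph of text and 2 degrees of freedom. No new data, no additional children and no change to clinical procedures are needed. The covariates must be fixed in advance, because choosing them after seeing results by arm would invite bias.

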### 5. Data management

#### 5.1 Data collection and CRFs

The data collection of this study is based on paper CRF forms, and all data and its collection process will be completed under the supervision of the trial management center. After the trial is completed, all data and CRF forms will be provided to the principal investigator for long-term storage.

#### 5.2 Saving of test files

The trial documents will be archived securely and confidentially so that they can be reviewed for compliance at any time. The relevant medical documents of the subjects will also be archived in accordance with regulations and saved for the maximum period allowed by the medical institution. If the archive changes, the researcher and the study center need to report to the ethics committee and shall not destroy trial-related documents without the approval of the ethics committee.

#### 5.3 Data quality

The ethics committee and clinical trial institutions will regularly monitor the quality of the data, and the researchers will allow the monitors to obtain any trial-related data at any time.

### 6. Confidentiality principle

This study will take the following measures to strictly protect the privacy and personal

information of each subject: (1) Confidentiality measures and information security systems for sample providers have been established; (2) Samples and data are stored securely, and all samples and data in the library are /or set access rights for data; (3) When samples or prepared research samples are transferred to other researchers or institutions, all collected samples shall be de-identified (coding management and deletion of all identification information); (4) Data resulting from the research may be published or published publicly, but name or personally identifiable information will not be released.

## 7. Quality control of research

### 7.1 Data Security Monitoring Board

The independent Data Safety Monitoring Board (DSMB) will monitor the entire process of this trial. All serious adverse events must be reported to DSMB. If serious clinical safety risks arise, DSMB will give specific opinions to the principal investigator and clinical trial institution. Including 1) continue the trial; 2) continue the trial after adjustment; 3) terminate the trial.

### 7.2 Researchers and training

Before the trial begins, researchers who can maximize the safety and compliance of the subjects will be selected based on their abilities and experience. In addition, only trained researchers who are familiar with the protocol can participate in this study, and training records will be stored in files.

### 7.3 Research monitoring

After the study begins, regular monitoring will be conducted to evaluate the progress of the study, adequacy of records, and compliance with the study protocol, and corresponding monitoring records will be provided to the investigators. In addition to regular on-site monitoring, remote monitoring will also be conducted to ensure timely submission of data. Monitors will maintain ongoing communication with researchers through written correspondence, telephone calls, or online conversations.

## 8. Ethical principles

### 8.1 Ethical approval

Research can only be implemented after approval by the Ethics Committee. During the research process, the research plan and operating procedures must be strictly followed. At the same time, modifications to the research plan and informed consent must be reviewed and approved by the Ethics Committee before execution.

### 8.2 Informed consent

Before each research subject is selected for this study, the researcher must provide him or his legal representative with a complete, comprehensive, easy-to-understand content and explanation of the informed consent form approved by the ethics committee in writing, and give it to the research subject or their legal representatives who will be given sufficient time to consider whether to participate in this study. The

research can only be entered after the research subjects or their legal representatives sign the informed consent form. During the study, if new safety information causes significant changes in the risk/benefit evaluation, all updated new information should be provided to the subjects or their guardians and a new informed consent form should be signed.

#### 8.3 Risk-benefit analysis

This study will not bring risks to subjects beyond routine diagnosis and treatment. Most of the clinical outcomes in this study are determined based on questionnaires and routine clinical examination results, and only a small amount of additional blood is drawn from the subjects for the detection of inflammation and pain-related factors. Participants will not receive direct benefit from participating in this study, but if participants are assigned to the intervention group, the intervention may reduce the occurrence of postoperative pain, but it may also have no effect. At the same time, the follow-up personnel during the follow-up period will provide you with treatment and healthcare-related suggestions based on the subject's condition. Subject participation may help us identify safer or more effective diagnosis and treatment methods and expand new scientific knowledge.

#### 8.4 Conflict of interest

not involving

#### 8.5 Subject protection measures

Participants are not required to pay any research-related costs for participating in the study. Subjects' de-identified information and de-identified biological samples may be used to create products or provide health-promoting services. If these situations occur, we will not inform the subjects, pay the subjects, or provide any compensation to the subjects or their families. Most uses of biological samples and biological information do not result in a commercial product or benefit to anyone. No remuneration or compensation will be provided to the subjects in this study.

When the subject's health condition is harmed while participating in this study, the researchers are informed, and we will take necessary measures in a timely manner and determine compensation or compensation liability in accordance with the relevant laws and regulations of our country.

### 9. Pre-assessment of project risks and risk treatment plan

Investigator reports SAE to the ethics committee

If an SAE occurs during the study, the investigator should immediately report all serious adverse events to the sponsor in writing (within 24 hours after the investigator learns of the event), and then provide a detailed and written follow-up report in a timely manner. At the same time, researchers must fill in the "Serious Adverse Event Report Form" to record the time of SAE occurrence, symptom description, severity, duration, measures taken, outcomes, basis for correlation assessment, and possible explanations for SAE,

etc. If the researcher is unable to learn of a serious adverse event in time (for example, the subject was first treated in another hospital), he or she should report and record the time when the serious adverse event was first learned within 24 hours after becoming informed.

Typically, this information should include a detailed description of the serious adverse event to allow for a complete medical evaluation of the event and an initial independent determination of the possible cause. In addition, information must be provided on other possible causes, such as concomitant medications and concomitant diseases. In the event of death of a subject, the autopsy report must be submitted as soon as possible if available.

#### Researchers report SUSAR to ethics committee

Researchers should promptly sign and read the relevant safety information of clinical trials such as Suspicious and Unexpected Serious Adverse Reactions (SUSAR) provided by the sponsor, consider the subject's treatment, whether to make corresponding adjustments, and communicate with the subject as soon as possible if necessary , and the SUSAR provided by the sponsor should be reported to the ethics committee.

#### 9.1 Adverse events (AEs)

All AEs need to be reported regardless of whether they occur related to trial procedures or drugs. At the same time, researchers need to follow up closely to determine whether they are related to trial procedures or drugs, patients' clinical outcomes, and whether they can be upgraded to serious adverse events (SAEs). This follow-up process needs to continue until the AEs and their related symptoms are reasonably controlled to a stable level.

